9.4.2 Methods of Analyses

9.4.2.1 General Considerations

Summary statistics will be computed by treatment group and visit. For continuous endpoints, the following descriptive statistics will be computed: number of observations, means, medians, standard deviations, standard errors, first and third quartiles, minimums and maximums, and 2-sided 95% CIs of the means (CIs will be provided for efficacy endpoints only). For categorical endpoints, the summaries will contain the number and percentage of subjects in each category.

The primary analysis method utilizing a repeated measures linear mixed effects model will include all observed data regardless of treatment adherence.

A sequential testing procedure will be used to maintain the family-wise type 1 error $\alpha = 0.05$ between the primary and secondary endpoints following the prespecified order below. An endpoint will only be tested for statistical significance if the endpoint tested in the previous step is statistically significant at 2-sided significance level of 0.05.

1. Primary endpoint: change from baseline in mean monthly hours of at least moderate headache pain intensity over months 1, 2, and 3

- 2. Secondary endpoints: change from baseline in mean monthly function domain score over months 1, 2, and 3, as measured by the MFIQ using the Hochberg procedure
 - Impact on physical functioning
 - Impact on usual activities
 - Impact on emotional functioning
 - Impact on social functioning
- Secondary endpoint: change from baseline in mean monthly average duration of at least moderate pain intensity in migraine attacks occuring over months 1, 2, and 3 (migraine attacks as defined in Section 11.1)
- 4. Secondary endpoint: change from baseline in mean monthly average peak migraine pain intensity over months 1, 2, and 3, as assessed by the 11-point NRS

Endpoint	Statistical Analysis Methods
Primary	The primary endpoint will be analyzed using a linear mixed effects model including treatment group, baseline value, scheduled visit, and the interaction of treatment group with scheduled visit, without any imputation for missing data.
Secondary	The secondary endpoints will be analyzed using a linear mixed effects model including treatment group, baseline value, scheduled visit, and the interaction of treatment group with scheduled visit, without any imputation for missing data.
Exploratory	Detailed primary analysis method for exploratory endpoints will be described in the SAP.

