5.1 Definition of Terms Included in Study Endpoints

5.1.1 Efficacy Endpoints Based on Daily Diary Data Collection During M-DBTP

During the 4-week baseline period and the 12-week M-DBTP, headache start and stop date/time, pain feature/symptoms, acute headache medication and aura related information will be reported on a daily basis via optional any-time diar(ies) (available 24 hours) and mandatory evening diary (only available once daily from 17:00 to 23:59).

Acute Headache Medication (AHM)

Acute headache medications collected in the eDiary are classified separately as follows:

	Medication Group A
Acute headache medication (AHM)	Ergotamine-Based Migraine Medications
	Triptan-Based Migraine Medications
	Gepant-Based Migraine Medications
	Ditan-Based Migraine Medications

Non-Opioid Acute Headache Medications
Non-Opioid Butalbital Containing Medications
Opioid-Containing Acute Headache Medications
Opioid-Containing Butalbital Containing Medications

	Medication Group B
	Ergots
	Triptans
	Gepants
Acute headache medication	Ditans
(AHM)	Opiate or opioid-containing medication
	Opioid Combination-analgesic
	Non-opioid Combination-analgesic
	Simple analgesics/NSAIDs

Acute Migraine-specific Medication (AMSM)

A subset of acute headache medication consisting of triptan-based migraine medications and ergotamine-based migraine medications

Medication Overuse (MO)

Monthly acute headache medication days meeting at least one of the following criteria based on medication category B:

- \geq 10 days of triptans
- \geq 10 days of ergotamines
- ≥ 10 days of opiates or opioid-containing medications or opioid combination-analgesics
- \geq 10 days of non-opioid combination-analgesics
- ≥ 15 days of simple analgesics/NSAIDs if no other acute headache medications were used
- ≥ 10 days of a combination of triptans, ergotamines, opiates or opioid-containing meds or opioid combination-analgesic, non-opioid combination-analgesic medications or simple analgesics/NSAIDs whilst not satisfying medication overuse criteria in any of the individual medication categories alone

Number of Diary Days in a Monthly Interval	Monthly Days with Medication Use
• ≥ 14 days	Prorate to 28-day equivalent without rounding Number of observed days with medication use*28/number of (diary days or medication days) within each monthly interval
• < 14 days	Set to missing

Qualified Headache

A qualified headache is defined as

- A headache of duration \geq 30 minutes, or

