- A headache with acute headache medications (migraine-specific or not) taken during the headache (start time and end time inclusive) with any length of duration, or
- An aura during which an acute migraine-specific medication is administered

Headache Day

A calendar day (00:00 to 23:59) in which the subject experiences \geq 1 qualified headache

Qualified Migraine Headache

A qualified migraine headache should meet at least one of the following criteria:

- A headache of duration ≥ 30 minutes, and meeting ≥ 1 of the following criteria (a and/or b):
 - a) \geq 2 of the following pain features:
 - Unilateral
 - Throbbing
 - Moderate to severe (based on the 3-level categorical pain severity)
 - Exacerbated with exercise/physical activity
 - b) \geq 1 of the following associated symptoms:
 - Nausea
 - Vomiting
 - Photophobia and phonophobia
- A headache during which an acute migraine-specific medication is administered regardless of the headache duration, pain features, and associated symptoms
- An aura during which an acute migraine-specific medication is administered

Migraine Day

A calendar day (00:00 to 23:59) in which the subject experiences \geq 1 qualified migraine headache

Migraine-free Day

A calendar day (00:00 to 23:59) **of a diary day** in which the subject does not experience any headache and aura, photophobia, phonophobia, and nausea/vomiting, **and does**

not take any acute headache medication

Diary Day

A calendar day (00:00 to 23:59) with complete headache, aura, and acute headache medication data recorded **via daily evening diary**

Information Day

A calendar day (00:00 to 23:59) which is either a headache day or a diary day

Migraine Attack in M-DBTP

A migraine attack is an episode of any qualified migraine headache. The following rules will be used to distinguish an attack of long duration from 2 attacks, or to distinguish between attacks and relapses:

- A migraine attack that is interrupted by sleep, or temporarily remits, and then recurs within 48 hours (recurrence time headache start time ≤ 48 hours) will be counted as 1 attack
- An attack treated successfully with medication but with relapse within 48 hours (recurrence time headache start time ≤ 48 hours) will be counted as 1 attack

Triptan-treated Migraine Attack in M-DBTP

A migraine attack with triptan taken during the attack (start time and end time inclusive)

Headache Pain Intensity (evaluated by NRS) in M-DBTP

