Worst or peak pain intensity collected on a headache ranges from 0 to 10 with a higher score indicating more severe pain.

Pain intensity is reported when the headache end time is reported or in an evening diary on a daily basis for an ongoing headache. Therefore, there can be multiple pain intensity values reported for a headache that lasts for multiple days. In some circumstances, a headache which starts and ends on the same day may also have up to 2 pain intensity values reported when the headache ends after evening diary completion: 1) pain intensity is reported in the evening diary for the period between headache start time and diary completion time; 2) pain intensity is reported either in any-time diary or the next day's evening diary for the period between previous diary completion time and headache end time. The NRS headache pain intensity will be used to assess the monthly average peak pain intensity.

Headache Pain Intensity (3-level)

Worst or peak pain intensity collected on a headache in 3 levels (mild, moderate or severe) followed by the NRS pain intensity question when the preceding NRS headache pain intensity is reported to be \geq 4, worst or peak pain intensity (3 levels) is set as mild if NRS headache pain intensity is reported to be <4.

Duration of Headache With at Least Moderate Pain Intensity

Duration of headache with at least moderate pain intensity (in hours and minutes) will be collected only when "Moderate" or "Severe" intensity is reported based on the 3-level headache pain intensity scale.

Monthly Migraine Days (MMD)

Number of migraine days during one monthly interval as defined below.

Number of Diary Days in a Monthly Interval	Monthly Migraine Days
• ≥14 days	Prorate to 28-day equivalent without rounding Number of observed migraine days*28/number of (diary days or migraine days) within each monthly interval
• < 14 days	Set to missing

Monthly Headache Days (MHD)

Number of headache days during one monthly interval as defined below.

Number of Diary Days in a Monthly Interval	Monthly Headache Days
● ≥ 14 days	Prorate to 28-day equivalent without rounding
	Number of observed headache days*28/number of information days
	Note: An information day is either a headache day or a diary day.
• < 14 days	Set to missing

Monthly Hours of at Least Moderate Headache Pain Intensity

Number of Diary Days in a Monthly Interval	Monthly Hours of at Least Moderate Headache Pain Intensity

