• ≥ 14 days	Prorate to 28-day equivalent without rounding Sum of hours of headaches with at least moderate pain intensity *28/number of (diary days or days with headache pain intensity) within each monthly interval
• < 14 days	Set to missing

Monthly Hours of at Least Moderate Headache Pain Intensity of Qualifying Oral Triptan Treated Migraine Attacks

Number of Diary Days in a Monthly Interval	Monthly Hours of at Least Moderate Headache Pain Intensity of Qualifying Oral Triptan Treated Migraine Attacks
• ≥14 days	Prorate to 28-day equivalent without rounding Sum of hours of at least moderate pain intensity of qualifying oral triptan treated migraine attacks *28/number of (diary days or migraine days) within each monthly interval
• < 14 days	Set to missing

Monthly Average Duration of at Least Moderate Pain Intensity in Migraine Attacks

Number of Diary Days in a Monthly Interval	Monthly Average Duration of at Least Moderate Pain Intensity in Migraine Attacks
• ≥14 days	Sum of all the reported duration with at least moderate headache pain intensity within an attack divided by number of attacks in each month If there is no migraine during the monthly interval, then the monthly average duration will be set to 0.
• < 14 days	Set to missing

Monthly Average Duration of at Least Moderate Pain Intensity in Qualifying Oral Triptan Treated Migraine Attacks

Number of Diary Days in a Monthly Interval	Monthly Average Duration of at Least Moderate Pain Intensity in Qualifying Oral Triptan Treated Migraine Attacks	
• ≥ 14 days	Sum of all the reported duration with at least moderate headache pain intensity within a qualifying oral triptan-treated attack divided by number of qualifying oral triptan-treated attacks in each month;	
	If there is no migraine during the monthly interval, then the monthly average duration will be set to 0.	
• < 14 days	Set to missing	

Monthly Average Peak Migraine Pain Intensity

Number of Diary Days in a Monthly Interval	Monthly Average Peak Migraine Pain Intensity
• ≥14 days	Sum of observed highest pain intensity scores (NRS) per migraine day divided by total number of migraine days with at least one measure of NRS; If there is no migraine day with NRS during the monthly interval, then the monthly average peak migraine pain intensity will be set to 0.
● <14 days	Set to missing

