8.3 Handling of Missing and Incomplete Data

Subjects may miss specific data points for a variety of reasons. In general, data could be missing due to a subject's early withdrawal from the study, a missed visit, or inability to evaluate an endpoint at a time point. For this study, efficacy endpoints will be collected via eDiary and subjects could miss entering several days of data in each monthly interval. The general procedures outlined below describe how missing data will be handled.

For the endpoints derived from the daily diary data, please refer to proration approach specified in Section 5.1.1 on handling missing daily diary data. Missing monthly measurement after proration will be handled by statistical analysis approaches listed in Section 9.5.

For the endpoint derived from the episodic diary data, missing data at timed assessment will be handled by statistical analysis approaches listed in Section 9.5.

Missing items in each clinical outcome assessment questionnaire will be handled based on the scoring algorithm for each assessment. The missing value in the algorithm derived measurements (eg, total score, domain scores) will be handled by statistical analysis approaches listed in Section 9.5.

Missing data in safety endpoints will not be imputed except for incomplete start date of an AE or concomitant medication, which will be imputed as follows:

	Missing	Imputation	Exception on adverse event start date
Start date (AE, concomitant medication)	Day	01	Default to Study Day 1 if an adverse event started the same year and month as Study Day 1 and the flag indicates that the adverse event started on or after the first dose of investigational product on the Events eCRF
	Day/Month	01 JAN	Default to Study Day 1 if an adverse event started the same year as Study Day 1 and the flag indicates that the adverse event started on or after the first dose of investigational product on the Events eCRF
	Day/Month/Year	No imputation	-

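### SAP 5.1.1, read literally, scores monthly peak migraine pain as 0 when a migraine headache was reported but no NRS was recorded; that month should be missing

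*SAP*

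**What the plan says.** SAP 5.1.1 derives the monthly value, in months with at least 14 diary days, as the sum of the highest daily NRS scores divided by the "total number of migraine days with at least one measure of NRS". The zero rule that follows reads, in part: "no migraine day with NRS during the monthly interval, then the monthly average peak migraine pain intensity will be set to 0". With fewer than 14 diary days the month is missing.

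The two duration endpoints in the same section use a narrower condition: 0 applies only if the month had no migraine.

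On missing data, Protocol 9.4.2.1 analyses the secondary endpoints with a mixed model containing treatment, baseline, visit and the "interaction of treatment group with scheduled visit, without any imputation for missing data". SAP 8.3 agrees: "Missing monthly measurement after proration will be handled by statistical analysis approaches listed in Section 9.5". The zero footnote in Protocol Table 9-1 and SAP Table 3-1 is attached to the duration endpoint only. SAP Section 10 declares one departure from the protocol, and it is not this one.

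**The concern.** The zero condition depends on whether a score exists, not on whether a migraine occurred. It therefore treats two different situations alike: a month with nothing to rate, and a month with something to rate that was not rated. In the second, 0 is an imputation, and it is the best score on the scale.

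A false zero can only look like improvement. Inclusion criterion 110 requires at least 4 baseline attacks of at least moderate severity. SAP 5.1.1 asks for that grade only when the NRS is 4 or more. Every eligible subject therefore starts above 0.

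At stake is one confirmatory secondary endpoint, the last in the testing sequence. SAP 9.5.1 plans no sensitivity analysis for it. The by-visit minimums in SAP 9.1 and the histograms in SAP 8.5 might show zeros but would not tell the unrated months from the migraine-free ones. The exploratory version, limited to months with at least 1 migraine attack, has no derivation of its own, so it is unstated whether the zero rule applies there.

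**Working it through.** **Which months the condition covers** (at least 14 diary days, no migraine day with an NRS)

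| Month | Is 0 an observation? |
|---|---|
| No migraine day | Yes, by the endpoint's convention |
| Migraine days only through "An aura during which an acute migraine-specific medication is administered", no headache | Defensible: no headache pain to rate |
| A migraine headache reported, no NRS on any migraine day | No: the value is unobserved |

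**Can the third row occur?** The definitions do not exclude it. One qualifying route is "A headache during which an acute migraine-specific medication is administered regardless of the headache duration, pain features, and associated symptoms", so a headache can count without pain data. Headache information is "reported on a daily basis via optional any-time diar(ies) (available 24 hours) and mandatory evening diary". The monthly-migraine-day formula allows for migraine days that are not diary days. Against this, "Pain intensity is reported when the headache end time is reported or in an evening diary on a daily basis for an ongoing headache", and a single recorded NRS on any migraine day removes the case. The documents do not say whether the NRS item can be skipped.

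**The plan's own figure.** Inputs from SAP Table 3-1: effect 0.11, SD 0.44, two-sided 0.05, 288 per arm with 10% dropout.
- n = 288 × 0.9 = 259 per arm.
- 0.11 / (0.44 × √(2/259)) = 2.845.
- Power = Φ(2.845 − 1.960) = 81.2%, which reproduces the stated 81%.

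**Illustrative size of one false zero.** Assumptions: the unrecorded NRS, B, would have been 4 to 7; 0.11 is on the 0–10 scale; simple means over 259 × 3 = 777 subject-months per arm approximate the model estimate.
- Subject's 3-month mean: B/3 = 1.33 to 2.33 points.
- Arm mean: B/777 = 0.0051 to 0.0090, or 4.7% to 8.2% of 0.11.

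**Equal rate q in both arms, equal baselines.** Difference = 0.11 × (1 − q): 0.1098 at q = 0.2%, 0.1095 at 0.5%, 0.1089 at 1%. The mean difference barely moves.

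**Spread.** If affected months were independent and the planned SD contained no such zeros, SD = √(0.44² + B²q(1 − q)/3). For B = 4 to 7, power would be about 78% to 73% at q = 0.25%, and 70% to 55% at q = 1%. Both rates are invented for illustration.

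**Why these sizes cannot be taken at face value.** Suppose 5% of months were legitimately 0, independently, with an otherwise typical NRS of 6. Those zeros alone would give a 3-month-mean SD of √(0.05 × 0.95 × 36 / 3) = 0.75, already above 0.44. The planned 0.11 and 0.44 may therefore not be zero-coded 0–10 values. The table row states neither scale nor zero-coding.

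**Power after the correction.** If 1% or 2% of subjects were lost entirely, a worst case, power on the planning figures would be 80.8% or 80.4%.

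**The case against.** The strongest reply is that the problem month hardly exists. The NRS is requested at headache end or in the evening diary. A diary day requires complete headache data, and the month must have at least 14 such days. Every migraine day must lack a score. Waiving pain features for a drug-treated headache changes its classification; it does not say the NRS goes uncollected. The optional any-time diary is itself a place where the NRS is entered. The eDiary specification is not available here, so any rate is a guess. This stands, and it limits the point to a low-frequency case.

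A reader might also infer from the divisor that the SAP expects unrated migraine headaches. The documents do not support that: treated-aura days are migraine days with no headache to rate, and they explain both the divisor and perhaps the zero wording. But the wording is not restricted to them.

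SAP 8.5 also provides for confirming questionable values and permits ad-hoc sensitivity analyses of extreme values. These are discretionary. They do not change the rule, and a zero produced by the derivation may not look questionable.

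None of this makes 0 the right value in a month where a headache was reported and not scored.

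**Conclusion.** The point holds as a defect in a derivation rule. Where it applies, the rule substitutes the best possible score for a missing one, against the no-imputation analysis in the protocol and SAP 8.3, and more broadly than the parallel duration rule.

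Its practical size is probably small and cannot be established from the documents. The rate of affected months, the NRS level, and the scale and zero-coding behind 0.11 are all unstated, so the shift of 0.005 to 0.009 per false zero is illustrative only.

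Two stronger readings should be resisted. A reader might infer that the rule favours erenumab; under blinding there is no reason to expect different rates by arm, and the exposure is a chance imbalance of a few months. A reader might infer a material loss of power; that needs an assumed rate and an assumed scale that the documents do not supply. The primary endpoint and the other secondary tests are unaffected, because this endpoint is last in the sequence. Priority: minor.

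**What to change.** Reword the peak-pain rule in SAP 5.1.1, for months with at least 14 diary days:

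1. Set the value to 0 if the month has no migraine day, or if every migraine day qualifies only through the treated-aura criterion with no headache reported.
2. Set it to missing if at least one migraine day had a reported headache and no migraine day has an NRS.

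The split should rest on whether a headache was reported, not on the term qualified migraine headache. SAP 5.1.1 counts a treated aura as one, so an aura-only month would otherwise meet both clauses.

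3. For the exploratory version limited to months with at least 1 migraine attack, set a month with a reported migraine headache but no NRS to missing, and state that the zero rule is not carried over.
4. Report by arm the number of months set to 0 and the number set to missing for lack of an NRS.

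The cost is one reworded clause, one added sentence and one summary line. The downside is possibly a few more missing months, which the planned mixed model handles under missing-at-random. If no such month occurs, the secondary endpoint's results do not change.

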5.1.2 Efficacy Endpoints Based on Episodic Diary Data Collection During E-DBTP

During the 2-week run-in period and the 1-month E-DBTP at month 4, subjects experiencing a qualified triptan-treated migraine attack will report medication usage, pain intensity, the most bothersome symptom and corresponding severity using the episodic diary. A qualifying headache for reporting is a headache reaching at least moderate pain intensity with initial triptan intake within 2 hours and also satisfying migraine headache criteria (ie, a qualified triptan-treated migraine attack). The initial triptan intake time (ie, time point 0) will trigger a 48-hour assessment window, during which the headache pain intensity, severity of the most bothersome symptom at 30, 60 and 120 minutes, 24 hours and 48 hours post triptan will be collected. Another 48-hour assessment window will be triggered if there is a new qualified triptan-treated migraine attack starts after the previous assessment window.

Headache Pain Intensity (NRS) in E-DBTP

Worst or peak pain intensity collected on a headache ranges from 0 to 10 with a higher score indicating more severe pain.

NRS Pain intensity is collected when a qualified headache reaching at least moderate pain intensity with triptan intake within 2 hours and for the following timed assessments at 30 minutes, 1-hour, 2-hour, 24-hour and 48-hour diaries.

Migraine Rescue Medication

Migraine rescue medication for each qualifying triptan-treated attack is defined as any additional acute headache medication(s) taken during the 48-hour assessment window.

Migraine Recurrence Within 24 Hours Post-triptan

Pain intensity NRS = 0 at any of the 30-minute, 60-minute, and 2-hour timed assessments and pain intensity NRS \geq 4 at 24-hour timed assessment

Pain Relief at timed assessment post-triptan dose

Pain intensity NRS < 4 at the specific timed assessment (eg, 30 minutes, 60 minutes, or 2 hours post-triptan dose).

Pain freedom at timed assessment post-triptan dose

Pain intensity NRS = 0 at the specific timed assessment (eg, 30 minutes, 60 minutes or 2 hours post-triptan dose).

Achievement of 24-hour sustained pain freedom post-triptan dose

Pain intensity NRS = 0 at both 2-hour and 24-hour timed assessment without rescue medication taken post-triptan dose.

Most Bothersome Symptom

The most bothersome symptom can be selected among nausea, vomiting, sensitivity to light, or sensitivity to sound.

Severity of Most Bothersome Symptom (4-level)

Worst or peak severity collected on the most bothersome symptom according to 4 levels (none, mild, moderate or severe)

Achievement of freedom from the most bothersome symptom at timed assessment post-triptan dose

Symptom severity = none at the specific timed assessment (eg, 30 minutes, 60 minutes or 2 hours post-triptan dose).

Achievement of relief from the most bothersome symptom at timed assessment post-triptan dose

Reduction in symptom severity by at least one level down (eg, from severe to moderate, mild to none) at the specific timed assessment (eg, 30 minutes, 60 minutes or 2 hours post-triptan dose).

5.1.3 Efficacy Endpoints Based on Monthly Data Collection Migraine Functional Impact Questionnaire (MFIQ)

The MFIQ version 2.0 is a self-administered 26-item instrument measuring the impact of migraine on broader functioning including 4 domains: Impact on Physical Functioning (5 items), Impact on Usual Activities (10 items), Impact on Social Functioning (5 items), and Impact on Emotional Functioning (5 items). In addition, there is 1 stand-alone global item assessing the overall impact on usual activities. Subjects respond to items using a 5-point scale assigned scores from 1 to 5, with 5 representing the greatest burden. Each domain score will be calculated as the sum of the item responses and the sum will be rescaled to a 0 to 100 scale, with higher scores representing greater burden. The recall period is the past 7 days and will be collected monthly at day 1, weeks 4, 8 and 12.

Migraine Symptom Severity Scale (MSSS)

The MSSS is a 7-item questionnaire that assesses frequency of pain and other symptoms associated with migraines. Responses are as follows: "never", "rarely", "less than half the time", "half the time or more", and "all or nearly all of the time". The responses are given a value from 0 to 3: Never = 0, Rarely = 1, Less Than Half the Time = 2, Half the Time or More = 3, and All or Nearly All of the Time = 3. The MSSS score is the sum of the responses to the 7 items with a range from 0 to 21. MSSS will be collected monthly at day 1, weeks 4, 8 and 12.

Most Troublesome Symptom (MTS)

The MTS will be measured by 5 questions on day 1 and the change in the MTS will be assessed by 2 questions at week 12. The baseline questions will be asking the subjects to select the most troublesome symptom during and/or between migraine headache attacks and to rate how often they experience the symptoms. The week 12 questions will be asking the subjects to rate how their previously identified most troublesome symptom during and/or between migraine headache attacks have changed since the start of the study on a scale of 1 (Very Much Improved) to 7 (Very Much Worse). Achieving 1 = Very Much Improved or 2 = Much Improved is considered as meaningful improvement.

Only subjects with non-missing baseline will be considered in the analysis. As per questionnaire design, if a subject answer 'No' for question 3 at baseline, subject will not be considered for between migraine headache attacks analysis.

Patient Global Impression of Severity (PGI-S)

The PGI-S is a single question that rates the severity of the subject's condition at the time of assessment. It is a 7-point scale that ranks severity of illness using one of the following response categories: 1 = Normal, not at all ill, 2 = Borderline ill, 3 = Mildly ill; 4 = Moderately ill, 5 = Markedly ill, 6 = Severely ill, and 7 = Most extremely ill. PGI-S will be collected at day 1 and week 12.

Migraine Interictal Burden Scale (MIBS-4)

The MIBS-4 measures interictal migraine-related burden with 4 questions that assess impairment in work or school, impairment in family and social life, difficulty making plans or commitments, and emotional/affective and cognitive distress. Each of the 4 questions is responded to using 1 of 6 response categories: "Don't know/NA" (Score = 0), "Never" (Score = 0), "Rarely" (Score = 1), "Some of the time" (Score = 2), "Much of the time" (Score = 3) or "Most or all of the time" (Score = 3). Response to each question is summed up to produce total score ranges from 0 to 12. The MIBS-4 total scores are categorized into 4 level of interictal burden: None (0), Mild (1 to 2), Moderate (3 to 4) and Severe (5 or higher). **MIBS-4** will be collected monthly at day 1, weeks 4, 8, 12 and 16.

Headache Impact Test (HIT-6)

The scoring of the HIT-6 total score will be performed using the QualityMetric's PRO CoRE Scoring Software. The HIT-6 total scores ranging from 36 to 78 can be categorized into 4 grades, representing little or no impact (49 or less), some impact (50 to 55), substantial impact (56 to 59), and severe impact (60 to 78) due to headache. HIT-6 will be collected monthly at day 1, weeks 4, 8 and 12.

Pain Catastrophizing Scale (PCS)

The PCS is a 13-item self-report measure consists of 3 subscales, which are Rumination (4 items), Magnification (3 items), and Helplessness (6 items). For each item, subjects are requested to provide a response in a 5-point Likert scale (0 "not at all," 1 "to a slight degree," 2 "to a moderate degree," 3 "to a great degree," 4 "all the time"). Higher scores in PCS indicate higher levels of catastrophizing. Response to each item is summed up to get the total score ranging from 0 to 52. PCS will be collected at day 1 and week 12.

